7.0 Site Selection

Centers will be selected for participation in the study and sub-study based on their ability to screen and enroll eligible patients, and perform the required study procedures outlined in section 9.0. SJM will attempt to have a diversified group of centers participating in the study, including academic and non-academic institutions, and anticipates participation to be in the order of approximately 25-30 percent from academic institutions. To ensure a widespread distribution of data and minimize site bias, a maximum of approximately 15% of the total enrollment will be allowed at a single site.

8.0 Patient Selection

8.1 Inclusion Criteria

Eligible patients will meet all of the following:

1. Have an approved indication, as per ACC/AHA/HRS/ESC guidelines, for implantation of an ICD or CRT-D system for treatment of heart failure or life-threatening ventricular tachyarrhythmia(s).
2. Have been implanted with a St. Jude Medical Optisure lead in the last 30 days or are scheduled for an Optisure lead implant.
3. Have the ability to provide informed consent for study participation and be willing and able to comply with the prescribed follow-up tests and schedule of evaluations.
4. Are 18 years or above, or of legal age to give informed consent specific to state and national law.

8.2 Exclusion Criteria

Patients will be excluded if they meet any of the following:

1. Enrolled or intend to participate in a clinical drug and/or device study, which could confound the results of this trial as determined by SJM, during the course of this clinical study.
2. Have a life expectancy of less than 5 years due to any condition.

8.3 Sub-study Enrollment Criteria

Patients enrolled in the main study who provide their consent to participate in the sub-study will be enrolled until 417 patients are enrolled.

9.0 Study Procedures

All required study procedures at each specified interval are outlined in the sections below.

Table 3: Schedule of Evaluations Summary

Evaluation	Enrollment*	Every 6 months thereafter until 5 years	24, 36, 48 and 60 month follow-up visits
Inclusion/Exclusion Criteria Evaluation	√		
Record capture threshold, signal amplitude, pacing lead impedance and high voltage lead impedance measurements on Optisure lead	√	√	
RV Lead Handling Characteristics (only applicable to patients enrolled at or before implant)	√		
Cinefluoroscopy (AP, LAO 45° or the best possible LAO view, RAO 45° or the best possible RAO view)			√**

* Enrollment can occur up to 30 days post implant

**Only applies to patients participating in the sub-study

9.1 Data Entry

Each study center will capture all study-related data and submit via an Electronic Data Capture (EDC) system. All study data will be entered and submitted through this system, including device data. The device session record data will be submitted through the SJM EDC system using the device data upload portal. The SJM EDC system complies with regulatory requirements to protect patient privacy and maintain data integrity.

Patient-specific device print-outs may be placed in the provided Patient Binders. Alternatively, print-outs may be stored electronically on the thumb drive provided to the centers specifically for the purpose of data collection and retention. The thumb drives will be stored in a secure location and made available to the sponsor representatives as required. The thumb drives will be returned or destroyed at sponsor request at the end of the study. All other study training material will be placed in the provided study Regulatory Binder.

Training for the EDC system will be provided by SJM.

9.2 Enrollment Requirements

9.2.1 Enrollment

Patients will undergo screening evaluations as outlined by the inclusion/exclusion criteria. To ensure enrollment of a diverse patient population into the Optisure lead study, centers will be instructed to approach and invite all patients who meet all of the inclusion and none of the exclusion criteria for participation in the study.

Data will be collected on the patient's gender, age, indication for device implantation, NYHA functional classification, and left ventricular ejection fraction.

Patients who meet inclusion/exclusion criteria, sign an IRB/MEC approved informed consent, and have an Optisure lead implant or attempted implant of the Optisure lead will be considered enrolled in the study. Enrolled patients who provide consent to participate in the sub-study will be included in the sub-study.

The following electrical measurements* must be performed: capture threshold testing for all implanted leads, signal amplitude measurements for the RV and RA leads, pacing lead impedance for all implanted leads and high voltage lead impedance for all implanted leads.

***Notes**

1. If the patient is in atrial fibrillation or atrial flutter, RA electrical measurements are not required.
2. If the patient is pacemaker dependent, RV sensing amplitude is not required.
3. As referenced under the Definitions in section 4.2, abnormal pacing lead impedances are defined as measured pacing impedances with values $\leq 200 \Omega$ or $\geq 2000 \Omega$. RV lead pacing impedances have been observed in typical clinical settings to be in the range of 200-1200 Ω for the majority of patients. However, lead pacing impedances measured up to 1999 Ω are considered to be within the normal bounds of the performance of the RV lead because characteristics such as non-

viable myocardium, lead-to-tissue contact, etc., specific to each patient have been known to produce measured pacing impedances that are higher than the observed 1200 Ω noted above.

Device diagnostics and archives of RV lead impedance values may also be used to diagnose potential lead failures. Alternatively, investigators should consult the respective device and lead user manuals, St. Jude Medical technical support or other St. Jude Medical clinical support personnel to diagnose potential lead failures.

The enrollment date for patients in the study will be the date when all protocol defined enrollment procedures (consent, implant and lead measurements) are completed.

Complete an Enrollment, Implant and Lead Measurements Case Report Forms and record all results. Complete an Adverse Event Case Report Form (if applicable) for all adverse events which occurred since the implant of the Optisure lead. Submit the forms to St. Jude Medical using the EDC system. Complete an Out of Service Form for any product used but not implanted (e.g. contaminated, dropped or opened in error).

Upload the device session record including all stored IEGMs to St. Jude Medical using the SJM EDC Portal device data upload utility. If the patient is enrolled after implant, provide the session record from the enrollment visit.

9.2.2 Unsuccessful Implant– if applicable

Enrolled patients who have an unsuccessful implantation of a St. Jude Medical Optisure lead (see definition for successful Optisure lead implant in section 4.2) will be followed for a period of 30 days for adverse events and then withdrawn from the study unless the implant will be re-attempted within 30 days of the unsuccessful implant. The physician may re-attempt the implantation of a St. Jude Medical Optisure lead at his/her discretion.

In addition to the Forms identified in section 9.2.1 complete the Out of Service for any product used but not implanted (e.g. contaminated, dropped or opened in error) and record all results. After 30 days, if the patient has not had an implant re-attempted, complete a Withdrawal Case Report Form and record all results. Submit the forms to St. Jude Medical using the EDC system.

If the physician chooses to re-attempt the implantation of a St. Jude Medical Optisure lead within 30 days, complete Implant and Lead Measurements Case Report Forms, an Adverse Event Case Report Form (if applicable) and Out of Service Case Report Form (if applicable) and record all results. Submit the forms to St. Jude Medical using the EDC system.

9.3 System Revisions – if applicable

If the system revision procedure occurs more than 3 months after implant then obtain cinefluoroscopy views of the entire length of the implanted leads before repositioning or explanting the Optisure lead. Cinefluoroscopy should be performed in three views (AP, LAO 45° or the best possible LAO view, RAO 45° or the best possible RAO view) and submitted to St. Jude Medical. If the patient is unwilling then the imaging is not required.

For all lead revisions (e.g. replacement or repositioning of the lead) complete the applicable testing as outlined in section 9.2.1. Any explanted pulse generator or leads (including damaged leads, lead segments and lead fragments) should be returned to St. Jude Medical for analysis promptly.

Any changes to the status of a lead (i.e., capped, removed) will be documented on the Product Out of Service Case Report Form. Complete an Adverse Event (if applicable), System Revision, Imaging (if applicable), and Out of Service for any product used but not implanted (e.g. contaminated, dropped or opened in error) Case Report Form. Submit the forms to St. Jude Medical using the EDC system.

9.4 Follow-Up Requirements

Lead measurements and adverse events (if applicable) will be obtained every 6 months from patients who have a successfully implanted Optisure lead until they reach the 5 year follow-up.

The schedule of follow-ups is based on the date of a successful Optisure lead implant. Table 4 outlines the time window that is permitted for each of the study interval visits.

Table 4: Study Interval Time Windows

Every 6 months thereafter until 5 years
± 90 days

The following electrical measurements* will be obtained at each follow up: capture thresholds for all implanted leads, signal amplitude measurements for the RV and RA leads, pacing lead impedance for all implanted leads and high voltage lead impedance for all implanted leads.

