4.0 Clinical Protocol

4.1 Study Design and Scope

The Optisure lead study is a multi-center, post-approval study that will be performed in compliance with the Conditions for Approval, as agreed upon with the FDA. Patients will be permitted to enroll in the study up to 30 days post-implant of the Optisure lead. Following a successful implant, patients will be followed every 6 months until 60 months (5 years). After patients complete 60 months of follow-up, their participation in the study will end. Patients who are consented prior to implant and for whom an implant is unsuccessful will be followed for 30 days for any adverse events and then withdrawn from the study, or may have an implant reattempted if the physician and patient choose to do so.

Patients who meet inclusion/exclusion criteria, sign an IRB/MEC approved informed consent, and have an implanted Optisure RV lead or attempted implant of the Optisure RV lead will be considered to be enrolled in the study. A total of 1725 patients will be enrolled at a maximum of 60 centers. Enrollment is expected to be completed between 20 and 24 months depending on the rate of enrollment.

Enrollment will be proportional to actual sales, and enrollment duration will not exceed 24 months. If implantation at the study sites is higher than the projected estimates (see section 4.5), then the study enrollment period will be decreased proportionately. Reporting will occur per section 6.0 of the protocol. In order to accomplish this, the study will be conducted at a maximum of 60 study centers.

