5.0 Study Outcome Measures

5.1 Primary Outcome Measure

5.1.1 Freedom from RV Lead Related Complications

The primary outcome measure for the Optisure Lead Post Approval study is the complication free survival rate at 5 years for complications related to the Optisure RV leads.

The hypothesis is as follows:

H0: Complication free survival at 5 years \leq 92.5%

H1: Complication free survival at 5 years $>$ 92.5%

The desired outcome is to reject the null hypothesis. The null hypothesis will be rejected at the 5% significance level if the 95% Lower Confidence Bound (LCB) for the freedom from complications is greater than 92.5%.

Sample Size

Assuming that the time to first complication follows an exponential distribution and the complication-free survival at 5 years is 95%, a sample size of 645 patients provides 80% power to reject the null hypothesis of 92.5% complication-free survival years at the 5% significance level (See Appendix D for detailed sample size calculations).

Patient Group

All patients who had an attempted implant of the Optisure RV lead will be included in the analysis of this endpoint.

Analysis

All complications will be classified as related to the Optisure RV lead or unrelated.

The following complications will be included in this analysis:

- Cardiac perforation
- Lead dislodgement that occurred greater than 30 days after implant
- Lead insulation damage
- Lead fracture
- Abnormal RV lead performance (abnormal lead defibrillation impedance, abnormal lead pacing impedance, elevated pacing thresholds, loss of capture, failure to deliver therapy, loss of sensing, oversensing, undersensing)

- Other unexpected complications that are considered related to the RV lead

The survival time for all patients will be calculated as the number of days from implant or attempted implant to the date the complication was first discovered. For patients who do not experience a complication related to the Optisure RV lead at the time of their withdrawal, the survival time will be censored on the date of their withdrawal. For patients who have not experienced any complication related to the Optisure RV lead at the time of analysis, the survival time will be censored on the date of analysis. The endpoint will be evaluated using the Kaplan-Meier method and the 95% lower confidence bound (LCB) will be obtained by transformation from its log scale, based on Peto et al¹. The null hypothesis will be rejected if the 95% LCB is greater than 92.5%.

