# Power calculation for exponential assumption
p.nul <- 0.925
p.exp <- 0.95
l.exp <- -log(p.exp)/5

N <- seq(630,660,5)
P <- numeric(length(N))

for (i in 1:length(N)) {
  n <- N[i]
  l <- NULL
  for (j in 1:10000) {
    print(j)
    x <- data.frame(time=rexp(n, l.exp), event=1)
    s.fit <- summary(survfit(Surv(time, event)~1, data=x, conf.int=0.9,
    conf.lower="peto", conf.type="log-log"))
    idx <- sum(s.fit$time<=5)
    l <- c(l, ifelse(idx==0, 1, s.fit$lower[idx]))
  }
  P[i] <- mean(l>p.nul,na.rm=T)
}
res <- cbind(N, P)
dimnames(res)[[2]] <- c("N", "Power")
```

Output:

```
> cbind(N, Power)
[1,] 630 0.8257
[2,] 635 0.8046
[3,] 640 0.7909
[4,] 645 0.8324
[5,] 650 0.8132
[6,] 655 0.8067
[7,] 660 0.8399
```

Detailed Sample Size Calculations for Complication rate

The 95% confidence interval for the Binomial proportion is calculated based on the Clopper-Pearson exact Binomial method. For a given observed value x , of the random variable X , which has a Binomial(n, p) distribution, the 100(1- α)% confidence interval for p is given by (L, U), where ¹:

$$L = \begin{cases} 0 & \text{for } x = 0 \\ \frac{x}{x + (n - x + 1)F_{1-\alpha/2, 2n-2x+2, 2x}} & \text{for } 0 < x < n \\ \left(\frac{\alpha}{2}\right)^{1/n} & \text{for } x = n \end{cases}$$

$$U = \begin{cases} 1 - \left(\frac{\alpha}{2}\right)^{1/n} & \text{for } x = 0 \\ \frac{(x + 1)F_{1-\alpha/2, 2x+2, 2n-2x}}{(n - x) + (x + 1)F_{1-\alpha/2, 2x+2, 2n-2x}} & \text{for } 0 < x < n \\ 1 & \text{for } x = n \end{cases}$$

Simulations for safety endpoint:

For a particular sample size (n), generate 10,000 random binomial samples with $p = 0.4\%$. Calculate the 95% Clopper-Pearson confidence interval for each sample.

The mean of the 95% Upper Confidence Limit is estimated by the average UCL from the 10,000 samples.

The above process was repeated for different values of n , and the sample size was chosen as the smallest n such that the mean 95% UCL is no more than 1% for any sample size larger than n .

Simulations were carried out in R version 2.5.1 and the code is provided below:

```

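### The ±90-day window also covers the final 60-month visit, so a compliant patient may be last observed up to 90 days before the primary 5-year time point

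*Protocol*

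**What the plan says.** Section 9.4 schedules visits every 6 months from the date of successful implant and states: "Table 4 outlines the time window that is permitted for each of the study interval visits". Table 4 holds one row, ±90 days, for all of them up to 5 years. Section 10.0 treats a visit as missed only when it falls outside its window, so a 60-month visit held 90 days early is compliant.

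On the end of follow-up, section 4.1 says: "After patients complete 60 months of follow-up, their participation in the study will end". No section asks for a contact on or after the 5-year date when the last visit was early.

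The primary outcome in section 5.1.1 is "the complication free survival rate at 5 years for complications related to the Optisure RV leads", with time counted in days from implant or attempted implant. It is estimated by Kaplan-Meier, and success requires the Peto lower bound to exceed 92.5%. Withdrawn patients are censored at withdrawal. For patients still free of complications at analysis, "the survival time will be censored on the date of analysis". Study completion is not among the withdrawal reasons listed in section 16.0, although that list is not exhaustive.

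**The concern.** The test concerns survival at 5 years, yet the visit schedule allows the last observation to fall before that day. Section 11.0 directs events between visits to the next scheduled visit, and after the final visit there is none. A complication in the gap is recorded only if the site happens to learn of it.

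The consequence depends on how completers are censored:

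- **At the last visit.** Early completers leave the risk set before 5 years. The Peto variance uses the number at risk, so the lower bound drops and power is lost.
- **At the date of analysis.** The risk set stays full, but days that nobody observed are counted as free of complications, which favours the lead.

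The Appendix D simulation contains no censoring, so the stated power allows for neither.

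**Working it through.** **Inputs.** True 5-year survival 95%, goal 92.5%, 645 patients for 80% power (5.1.1). Total attrition about 52%: 1 − 0.62 × 0.78 = 0.516 (5.2.1). Enrolment 828 / 0.48 = 1725 (5.2.1). "The null hypothesis will be rejected at the 5% significance level", and the Appendix D code uses "data=x, conf.int=0.9", so the bound is one-sided 95% with z = 1.645. The analysis text says the "95% lower confidence bound (LCB) will be obtained by transformation from its log scale"; the code uses the log-log scale. Both are shown.

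**Formulas.** With S the Kaplan-Meier estimate and n the number at risk, the Peto standard error of ln S is √((1 − S)/n).
- Log scale: LCB = exp{ln S − 1.645 √((1 − S)/n)}.
- Log-log scale: the standard error is divided by |ln S| and the bound is formed on ln(−ln S).

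**The plan's own figure.** Without censoring, events by 5 years are Binomial(645, 0.05). On the log-log scale the trial succeeds with 37 or fewer events, an exact power of 0.8295 against 0.8324 in Appendix D. It reproduces. The log-scale bound gives 0.869.

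**Number at risk at 5 years.** With no early exit: 1725 × 0.48 × 0.95 ≈ 786. If half the completers have their final visit before 5 years: 786 / 2 = 393.

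**The bound at an observed S = 0.95.**
- n = 786: √(0.05/786) = 0.00798, so LCB = 93.8% (log) or 93.6% (log-log).
- n = 393: √(0.05/393) = 0.01128, so LCB = 93.3% (log) or 92.9% (log-log).
- The bound clears 92.5% with at least 191 at risk (log) or 294 (log-log).

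**Power, completers censored at the last visit.** Simulated with 1725 enrolled and exponential events and attrition; 4,000 trials per case, Monte Carlo error at most about 0.8 point. The protocol does not give the distribution of final visit dates, so a range is assumed. The bound is read either with the 5-year risk set or, as in the Appendix D code, at the last event before 5 years.

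| Final visits (assumed) | At risk at 5 years | Power read at 5 years, log / log-log | Power read at last event, log / log-log |
|---|---|---|---|
| None before 5 years | 786 | 96% / 93% | 96% / 94% |
| Normal, SD 30 days, within ±90 | 393 | 84% / 71% | 93% / 89% |
| Uniform over ±90 days | 393 | 85% / about 72% | 92% / 86% |
| 80% early | 157 | 40% / 7% | 85% / 77% |
| All at −90 days | 0 | no bound | 99% / 98% |

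The last cell is not reassuring. The estimate there is in effect survival at about 57 months, which under the null is 0.925^((5 − 90/365.25)/5) = 92.86%. Type I error for that case is 9.5% (log) or 6.6% (log-log).

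**Type I error at a true 92.5%, completers censored at the analysis date.**

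| Final visits (assumed) | Log / log-log |
|---|---|
| None before 5 years | 3.8% / 2.2% |
| Uniform over ±90 days | 4.6% / 2.6% |
| All at −90 days | 9.1% / 5.9% |

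The most that the unobserved time can hide under the null is 92.86 − 92.50 = 0.36 percentage point. With uniform visits the average unobserved time is 0.5 × 45 = 22.5 days per completer, or about 0.36 × 22.5/90 = 0.09 point.

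**The case against.** Four objections carry weight.

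1. Section 4.1 ends participation after 60 months of follow-up, and a patient seen at month 57 has not had 60 months. On this reading the window only defines an on-time visit and does not close the patient. That is a fair reading of 4.1, and section 11.0 does keep adverse event reporting open until withdrawal. But no contact is scheduled after an early final visit, so event status at 5 years is still not actively ascertained.

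2. The Appendix D code takes the bound at the last event before 5 years, where about 632 remain at risk under uniform visits. Power is then 92% or 86%, above the planned 80%. This stands, and it is why both readings are reported.

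3. The literal censoring rule keeps the risk set full (about 794 at 5 years with uniform visits), and type I error stays below 5% under uniform visits. This also stands. It replaces a loss of precision with unobserved event-free time, at a small cost unless visits run early.

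4. Censoring of completers may be settled in a statistical analysis plan that is not at hand. That is possible, but the visit window belongs to the protocol, and no analysis rule recovers observations that were never made.

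A reader might infer that the window empties the 5-year risk set. It does so only if every final visit is early; the window is two-sided, and a symmetric spread halves the set. A reader might also infer that section 4.5 forces early visits, because follow-up is shown as complete at month 84. That is a projected timeline (24 + 60 = 84), stated to be changeable, and not a data cut-off. It merely leaves no room for the late side of the window for the 1725 − 1440 = 285 patients planned for months 22 to 24.

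**Conclusion.** The gap is real and of moderate size. The protocol permits a compliant patient to be last observed up to 90 days before the time point of its primary test, and it gives no censoring rule that handles this well.

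Under a symmetric spread of visits, the cost is a drop in power to 85% (log) or about 72% (log-log) if the bound is read at 5 years with last-visit censoring, and to about 92% or 86% if it is read at the last event. Only the log-log reading at 5 years falls below the planned 80%. With analysis-date censoring, type I error stays under 5% for a uniform spread and exceeds it in the all-early case. The two harms are alternatives and do not add up.

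The documents do not support a claim that the trial is underpowered or its test invalid. Such a claim would need mostly early visits, which nothing in the protocol predicts, and enrolment of 1725, set by the secondary outcome's 828 rather than by 645, absorbs part of the loss. The figures rest on assumed visit dates and exponential attrition. This is an inexpensive improvement worth making, not a condition for the study to proceed.

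**What to change.** - In Table 4, give the 60-month visit its own window of 0 to +90 days from the 5-year date. Alternatively, keep ±90 days but require a documented lead-status and adverse-event contact on or after the 5-year date before a patient is closed as complete.
- In section 5.1.1, state that event-free completers are censored at their last observed date, not at the date of analysis.
- In section 4.5, let the projected end of follow-up allow for the late side of the window (84 + 3 = month 87) and move the later milestones to match.

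The cost is wording for one visit and one censoring rule. The window option adds no patients and no visits; the contact option adds one brief contact for patients seen early. The final report may move by up to 3 months, and some final visits become slightly harder to schedule.
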